5.2 Exclusion criteria

Patients eligible for this study must not meet **any** of the following criteria:

1. Pregnancy statements and contraception requirements:

Pregnant or nursing (lactating) women, where pregnancy is defined as the state of a female after conception and until the termination of gestation, confirmed by a positive hCG laboratory test.

Women of child-bearing potential, defined as all women physiologically capable of becoming pregnant (or female partners of male patients), unless they are using highly effective methods of contraception during dosing and for 3 months after stopping medication. Highly effective contraception methods include:

- Total abstinence (when this is in line with the preferred and usual lifestyle of the subject. Periodic abstinence (e.g., calendar, ovulation, symptothermal, post-ovulation methods) and withdrawal are not acceptable methods of contraception).
- Female sterilization (have had surgical bilateral oophorectomy with or without hysterectomy), or tubal ligation at least six weeks before taking study treatment. In case of oophorectomy alone, only when the reproductive status of the woman has been confirmed by follow up hormone level assessment.
- Male sterilization (at least 6 months prior to screening). For female subjects on the study the vasectomized male partner should be the sole partner for that subject
- Use of oral, injected or implanted hormonal methods of contraception or placement of an intrauterine device (IUD) or intrauterine system (IUS), or other forms of hormonal contraception that have comparable efficacy (failure rate $<1\%$), for example hormone vaginal ring or transdermal hormone contraception.

In case of use of oral contraception women should have been stable on the same pill for a minimum of 3 months before taking study treatment.

Sexually active males unless they use a condom during intercourse while taking the drug during treatment and for 3 months after stopping treatment and should not father a child in this period. A condom is required to be also used by vasectomized men as well as during intercourse with a male partner to prevent delivery of the drug via semen.

2. Evidence of active acute or chronic graft versus host disease (GVHD).
3. Evidence of any active malignancy.
4. Subjects who are human immune deficiency virus (HIV), hepatitis C virus (HCV), hepatitis B surface antigen (HBsAg) positive in screening visit.
5. Cytogenetic abnormality in chromosome 7 present before the allo-HSC.
6. Evidence of any clonal abnormality on cytogenetics (in bone marrow analysis).
 - A local post-transplant conventional cytogenetic assessment should be available within 8 weeks before Day 1.
 - If the cytogenetics is not valuable, i.e, it does not show metaphases, a FISH for MDS-related most frequent abnormalities including chromosome 7 is accepted.

As a consequence, patients with dry tap bone marrow aspiration are NOT eligible.

7. Evidence of bone marrow involvement or progression of the underlying disease assessed by the applicable methods in each case.
8. Evidence of thrombotic microangiopathy.
9. Evidence of possible causes of cytopenia other than PGF (active infections, myelotoxic drugs, hypersplenism...).
10. Prior use of any thrombopoietin receptor (TPO-R) agonists for PGF.
11. AST or ALT levels $>3 \times$ ULN.
12. Creatinine level $\geq 1.5 \times$ ULN.
13. Total bilirubin level $\geq 1.5 \times$ ULN.
14. Previous thromboembolic event (other than line-related upper extremity thrombosis)
15. Hypersensitivity to eltrombopag or its components.
16. Clinically significant ECG abnormality history or current diagnosis of cardiac disease indicating significant risk of safety for subjects participating in the study such as uncontrolled or significant cardiac disease or impaired cardiac function including any of the following:
 - a). Corrected QTc > 450 msec (male subjects), > 460 msec (female subjects) using Fredericia correction (QTcF) on the screening ECG
 - b). Myocardial infarction
 - c). Uncontrolled congestive heart failure
 - d). Unstable angina
 - e). Congenital long QT syndrome.
17. Administration of an investigational drug within 30 days or 5 half-lives, whichever is longer, preceding the first dose of study treatment.
18. Patient with liver cirrhosis.
19. Risk factors for Torsade de Pointes including uncorrected hypokalemia or hypomagnesemia.

20. Subjects with any serious and/ or unstable pre-existing medical, psychiatric disorder or other conditions that could interfere with patient's safety, obtaining informed consent or compliance with the study procedures as per investigator discretion.

6 Treatment

6.1 Study treatment

The study treatment for this trial is eltrombopag.

6.1.1 Dosing regimen

Table 6-1 Dose and treatment schedule

Study treatments	Pharmaceutical form and route of administration	Dose	Frequency and Regimen
Eltrombopag	Film-coated tablet for oral use	Administration at a daily dose of 150 mg (75 mg in Asian Ancestry participants). The maximum permissible dose of eltrombopag in this study will be 150 mg daily and 75 mg daily for Asian ancestry participants.	Daily

Patients will receive 150 mg of eltrombopag orally once daily up to 36 weeks. The starting dose will be 150 mg daily, except for Asian ancestry participants, in whom it will be 75 mg daily to adjust for the lower eltrombopag apparent clearance observed in this population.

Eltrombopag doses should be taken at least 2 hours before or 4 hours after any products such as antacids, dairy products, or mineral supplements containing polyvalent cations (e.g., aluminum, calcium, iron, magnesium, selenium, and zinc). Eltrombopag may be taken with food containing little (<50 mg) or preferable no calcium. If the patient forgets to take a dose, the dose should be restarted the next day at the usual time.

6.1.2 Treatment duration

The duration of treatment with eltrombopag will be based on the reasons described below and other reasons for early withdrawal ([Section 7.2.3.17.2.3.1](#)):

- If no partial or complete hematological response is observed at 16 weeks and maintained afterwards, the patient will be withdrawn from the study.
- In patients achieving complete response without transfusion support for a minimum of 8 weeks, the dose of eltrombopag may be reduced by 50%, and discontinued if counts remain stable after 8 weeks at the reduced dose. If relapse occurs after eltrombopag discontinuation, eltrombopag can be reintroduced at the last effective dosage.
- If new clonal cytogenetic abnormalities associated with dysplastic bone marrow findings are observed such as monosomy 7, eltrombopag should be permanently discontinued.

- If the patient develops myelodysplastic syndrome (MDS) or acute myeloid leukemia (AML) assessed by sensitive methods, eltrombopag will be permanently discontinued.
- If other non-clonal and/or cytogenetic abnormalities with uncertain meaning not previously observed and not associated with worsening blood counts or bone marrow dysplastic, the decision of discontinuing eltrombopag is up to the investigator, based on a more frequent bone marrow aspirate monitoring of cytogenetic abnormalities and dysplastic findings.
- If relapse of previous hematological disease occurs, eltrombopag will be permanently discontinued.
- If patient receives a new HSCT, eltrombopag will be permanently discontinued

6.2 Dose modifications

6.2.1 Dose modification and dose delay

For patients who do not tolerate the protocol-specified dosing schedule, dose adjustments are mandated to allow the patient to continue the study treatment. The daily dose of eltrombopag will be decreased to prevent thrombocytosis according to the following guidelines ([Table 6-2](#)).

All dose modifications should be based on the worst preceding toxicity. If study treatment is being held due to toxicity, scheduled visits and all assessments should continue as scheduled, except without dosing.

These changes must be recorded on the Dosage Administration Record CRF.

6.2.1.1 Dose modifications based on hematologic response

Table 6-2 Criteria for dose management of eltrombopag based on platelets count

The maximum permissible dose of eltrombopag will be 150 mg daily, except in Asian ancestry participants that will be 75 mg daily

Platelet count	Dose adjustment
>20,000/ μ L to 150,000/ μ L	Keep the same dose
150,000/ μ L to 250,000/ μ L	Decrease dosage by 25 mg every 2 weeks to lowest dose than maintains platelet count \geq 50,000/ μ L
>250,000/ μ L	Discontinue eltrombopag for one week, if platelet count falls to <100,000/ μ L; restart a dosage decreased by 25 mg/day

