7.3 Assessment types

7.3.1 Efficacy assessments

7.3.1.1 Overall hematologic response rate

The overall response rate corresponds to the percentage of patients who have a hematological response (partial and complete) by 16 weeks after the initiation of eltrombopag.

A partial hematologic response (PR) is defined when any of the following:

- Platelet count $\geq 20,000/\mu\text{L}$ (with platelet transfusion independence), confirmed in two consecutive blood tests separated a minimum of 7 days.
- Absolute neutrophil count (ANC) $\geq 1,000/\mu\text{L}$ (when pretreatment ANC was $< 1,000/\mu\text{L}$) confirmed in two consecutive blood tests separated a minimum of 7 days
- Hemoglobin $\geq 100\text{g/L}$ (when pretreatment Hb was $< 100\text{g/L}$) (with red blood cells (RBC) transfusion independence), confirmed in two consecutive blood tests separated a minimum of 7 days.

A complete response (CR) is defined when all three of the following:

- Platelet count $\geq 100,000/\mu\text{L}$ confirmed in two consecutive blood tests separated a minimum of 7 days
- Absolute neutrophil count (ANC) $\geq 1,500/\mu\text{L}$ (when pretreatment ANC was $< 1,000/\mu\text{L}$), confirmed in two consecutive blood tests separated a minimum of 7 days.
- Hemoglobin $\geq 110\text{ g/L}$ (when pretreatment Hb was $< 100\text{g/L}$), confirmed in two consecutive blood tests separated a minimum of 7 days.

Responses in each hematological lineage separately will be determined at weeks 16, 20, 24, 30 and 36 after the initiation of eltrombopag. In addition, secondary overall hematological

response outcomes (partial and complete) will be determined at 24 and 36 weeks after the initiation of eltrombopag.

Local evaluations will be used for laboratory tests (hematology and biochemistry), and whenever possible the same local laboratory will be used throughout the study so that the comparison is consistent.

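### Table 6-2 gives two conflicting dose instructions once a platelet-driven reduction brings the count to 50,000–150,000/µL, which puts the late platelet complete-response rates in SAP 10.2 at risk

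*Protocol*

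**What the plan says.** Protocol 6.2.1 gives the purpose of Table 6-2: "The daily dose of eltrombopag will be decreased to prevent thrombocytosis according to the following guidelines". The table in 6.2.1.1 has three rows:

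- Above 20,000 and up to 150,000/µL: "Keep the same dose".
- 150,000 to 250,000/µL: "Decrease dosage by 25 mg every 2 weeks to lowest dose than maintains platelet count" at or above 50,000/µL.
- Above 250,000/µL: stop for a week and, if the count falls below 100,000/µL, "restart a dosage decreased by 25 mg/day".

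A separate rule in Protocol 6.1.2 covers complete responders: "In patients achieving complete response without transfusion support for a minimum of 8 weeks, the dose of eltrombopag may be reduced by 50" per cent. It does not refer to Table 6-2.

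On the endpoint side, Protocol 7.3.1.1 states "A complete response (CR) is defined when all three of the following", and the platelet element is a confirmed count of at least 100,000/µL. For partial response, "A partial hematologic response (PR) is defined when any of the following" applies, and the platelet element is at least 20,000/µL without platelet transfusion. SAP 10.2 reports platelet complete response separately from platelet partial response at weeks 16, 20, 24, 30 and 36. SAP 10.1 (primary) and SAP 10.3 (weeks 24 and 36) pool partial and complete response.

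**The concern.** Row 2 is entered at 150,000/µL or more, but its end point is defined by a count of 50,000/µL. Following it to that end point means reducing further after the count has dropped into row 1, where the instruction is to leave the dose alone. Two sites can each follow the table as written and give different doses to patients with the same counts.

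The patients concerned are good platelet responders, who supply the numerator of the platelet complete-response rate. Whether such a patient sits above or below 100,000/µL at week 24 or 36 may depend partly on which row the site followed. Nothing in SAP 10.1 to 10.3 shows the reader when a platelet complete response ended after a dose reduction made under this table.

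**Working it through.** Table 6-2 contains no computed figure to reproduce. The check sets its rows and the response thresholds side by side.

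**1. Instruction and response status by count, during a row 2 step-down**

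| Count (/µL) | Row 1 | Row 2 | Platelet PR count (≥20,000) | Platelet CR count (≥100,000) |
|---|---|---|---|---|
| 150,000 exactly | keep | reduce | met | met |
| 100,000–149,999 | keep | continue while ≥50,000 holds | met | met |
| 50,000–99,999 | keep | continue while ≥50,000 holds | met | not met |
| below 20,000 | not covered | not covered | not met | not met |

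The rows disagree over the whole band from 50,000 to 150,000/µL. A count of exactly 20,000 is also outside every row, because row 1 starts above it.

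**2. Can the rows be read consistently?** Suppose the row is looked up afresh at each count. Row 1 then takes over as soon as the count is below 150,000/µL, and the 50,000 limit in row 2 matters only if a single 25 mg step takes the count from 150,000 or more to below 50,000. The limit would have almost no function. The protocol does not state this reading, and the purpose given in 6.2.1 does not settle precedence.

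**3. Largest dose gap between the readings**

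- From 150 mg, suppose the count drops below 150,000/µL after one step. The row 1 reading stops at 150 − 25 = 125 mg. The row 2 reading can go 125, 100, 75, 50, 25 mg, which is five steps. The gap is (125 − 25)/25 = 4 dose levels. Five steps have four intervals, so the fifth comes 4 × 2 = 8 weeks after the first.
- From 75 mg, the readings end at 50 mg and 25 mg, one level apart. The second step comes 2 weeks after the first.

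**4. Step interval against scheduled counts (Protocol Table 7-1).** Visits are 4 weeks apart from week 12 to week 24, then 6 weeks apart to week 36. At one step per 2 weeks, 4/2 = 2 steps (50 mg) or 6/2 = 3 steps (75 mg) fit into one interval between scheduled counts.

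**5. Overlap with the 6.1.2 rule.** A patient in sustained complete response with platelets of 100,000–150,000/µL may be reduced under 6.1.2, while row 1 says keep the dose.

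**6. Effect on the reported rates**

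- Platelet complete response (SAP 10.2): each patient moved below 100,000/µL changes the rate by 1/33 = 3.0 points, using the planned 33. The number of such patients is not in the documents. If it were 1 to 6 (an assumption), the shift would be 3.0 to 6/33 = 18.2 points. SAP section 3 also gives percentages of valid responses, and with missing counts each patient would weigh more there.
- Pooled partial-or-complete response (SAP 10.1 and 10.3): a count of 50,000/µL is 50,000/20,000 = 2.5 times the platelet partial-response threshold. If transfusion independence holds, a move from complete to partial response changes these rates by 0.

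**The case against.** The best defence is that clinicians will look up the row for the current count, and that the table exists to prevent thrombocytosis. That is a possible reading, but it is unstated and leaves the 50,000 limit nearly idle, so the conflict stands.

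The defence is right about the consequences, and four stronger inferences should be resisted:

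- A reader might infer that patients reduced under row 2 lose response and are withdrawn. The documents do not support this. Partial response needs one lineage only, and either row, followed as written, keeps a patient in the disputed band above the platelet threshold. Loss of response would need a count below 20,000/µL or renewed platelet transfusion, together with no neutrophil or hemoglobin response.
- A reader might infer that everyone above 150,000/µL is affected. While the count stays at 150,000–250,000 both readings reduce the dose, and above 250,000 row 3 applies. The readings part only when the count falls below 150,000 during a step-down.
- A reader might take the 50,000 limit as an error because it is half the 100,000 needed for platelet complete response. A dosing limit need not equal an efficacy threshold, and no section says that it should.
- A reader might want platelet complete response split by whether the dose was reduced. Reduced patients have, by definition, already reached at least 150,000/µL. The split would condition on a post-baseline response and could not separate loss through dosing from drug failure.

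It is also fair that a patient never reduced is already at the maximum permissible dose, so the missing row at 20,000 or less matters only after a reduction. SAP section 8 already reports dose modifications, their reasons and the duration at each dose.

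**Conclusion.** The contradiction is in the text: for 50,000–150,000/µL during a step-down, Table 6-2 gives two instructions and the protocol gives no precedence. Exactly 150,000 is covered twice, and 20,000 or less after a reduction is not covered.

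The statistical reach is narrow. It is mainly the platelet-lineage complete-response rate at weeks 16 to 36 in SAP 10.2, plus any breakdown of weeks 24 and 36 into complete and partial response. The size is 3.0 points per affected patient on a denominator of 33. The total is unknown, because the documents give neither a platelet dose-response relation nor the expected number reaching 150,000/µL. The four-level dose gap is a worst case: it needs a patient who falls below 150,000 after one step and still holds 50,000 down to 25 mg.

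The primary rate and the pooled maintenance rates should not move, provided that counts stay at 50,000 or more with transfusion independence. The clarification is still worth making, since it bears on consistent dosing across sites as well as on a reported secondary result.

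**What to change.** **Protocol.** The sponsor must reconcile the rows of Table 6-2 with each other, and with the complete-response taper in 6.1.2, so that every platelet count has exactly one instruction, including during a step-down, at exactly 150,000/µL, and at 20,000/µL or less after a reduction. The content is for the sponsor's medical team; this review takes no view on which instruction is right.

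**SAP 10.2.** Report best confirmed platelet complete response alongside the time-point rates. List the patients whose platelet complete response ended after a Table 6-2 reduction, with the dates, doses and counts around it. Label the listing as descriptive and make no comparison from it.

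**Cost.** One short protocol clarification, issued as a written amendment under Protocol 12.1, and one added rate and one listing in the SAP. No new data are needed: blood counts are collected at the scheduled visits, and dose changes are already recorded on the Dosage Administration Record.

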6.2.1.2 Dose modifications due to liver signals

Eltrombopag can cause hepatobiliary laboratory abnormalities, severe hepatotoxicity, and potentially fatal liver injury. Serum ALT, AST and bilirubin should be measured before initiation of eltrombopag, and at every clinic visit during the whole study. Abnormal serum liver tests should be evaluated with repeat testing as described in table 6-3. If the abnormalities are confirmed, serum liver tests should be monitored weekly until the abnormalities resolve, stabilize, or return to baseline levels. Please follow the dose modifications for isolated ALT/AST and bilirubin elevation described in [Table 6-3](#).

Table 6-3 Criteria for eltrombopag dose adjustment based on liver enzyme and bilirubin levels

Dose modifications for ETB115	
Worst toxicity CTCAE ^a Grade (value) during the treatment	
Investigations (Hepatic)	
Isolated Total Bilirubin elevation	
> ULN – 1.5 x ULN	Maintain dose level
> 1.5 - 3.0 x ULN*	
Interrupt dosing and weekly monitor LFTs^b, or more frequently if clinically indicated, until resolved to $\leq 1.5 \times$ ULN:
 
If resolved in ≤ 14 days, then resume at same dose level
 
If resolved in > 14 days, then decrease one dose level ^e

> 3.0 - 10.0 x ULN**	
Mandatory: Interrupt dosing and weekly monitor LFTs^b, or more frequently if clinically indicated, until resolved to $\leq 1.5 \times$ ULN:
 
If resolved in ≤ 14 days, then decrease one dose level ^e
 
If resolved in > 14 days, then discontinue patient from study drug treatment. LFTs^b will continue to be monitored weekly, or more frequently if clinically indicated, until total bilirubin has resolved to baseline or stabilization over 4 weeks.

> 10.0 x ULN**	
Mandatory: Discontinue patient from study drug treatment
 
The subject should be monitored weekly (including LFTs^b), or more frequently if clinically indicated, until total bilirubin have resolved to baseline or stabilization over 4 weeks.

Note: If total bilirubin $> 1.5 - \leq 3 \times$ ULN is due to the indirect (non-conjugated) component only, no changes to dose are required.** Note: If total bilirubin $> 3.0 \times$ ULN is due to the indirect (non-conjugated) component only, and hemolysis as the etiology has been ruled out as per institutional guidelines (e.g., review of peripheral blood smear and haptoglobin determination), then decrease 1 dose level ^e and continue treatment at the discretion of the investigator
	
Isolated AST or ALT elevation	
> ULN - 3.0 x ULN	Maintain dose level
> 3.0 - 5.0 x ULN	
Maintain dose level.
 
Repeat LFTs^b as soon as possible, preferably within 48-72 hours from awareness of the abnormal results.
 
If abnormal lab values are confirmed upon the repeat test, then monitor LFTs^b weekly, or more frequently if clinically indicated, until resolved to $\leq 3.0 \times$ ULN
 
Discontinue patient from the study treatment if elevation is combined with any of the following:
 
 • Clinical symptoms of liver injury or evidence for hepatic decompensation • Progressively increasing LFTs^b upon repeat testing • Persistence for ≥ 4 weeks

> 5.0 - 10.0 x ULN	Mandatory: Interrupt dose. Repeat LFTs ^b as soon as possible; preferably within 48-72 hours from awareness of the abnormal results. Monitor LFTs ^b weekly, or more frequently if clinically indicated until resolved to $\leq 3.0 \times$ ULN then: If resolved in ≤ 14 days, maintain dose level If resolved > 14 days, decrease one dose level ^e
> 10.0 - 20.0 x ULN	Mandatory: Interrupt dose. Repeat LFTs ^b as soon as possible, preferably within 48-72 hours from awareness of the abnormal results. Monitor LFTs ^b weekly, or more frequently if clinically indicated until resolved to \leq baseline. Then decrease one dose level ^e .
> 20.0 x ULN	Mandatory: Discontinue patient from study drug treatment. Repeat LFTs ^b as soon as possible, preferably within 48-72 hours from awareness of the abnormal results. Monitor LFTs ^b weekly, or more frequently if clinically indicated until resolved to \leq baseline or stabilization over 4 weeks.
Combined^c elevations of AST or ALT and total bilirubin	
For patients with normal baseline ALT and AST and total bilirubin value, [AST or ALT $> 3.0 \times$ ULN] combined with [total bilirubin $> 2.0 \times$ ULN] without evidence of cholestasis ^d OR For patients with elevated baseline AST or ALT [AST or ALT $> 3 \times$ baseline] OR [AST or ALT $> 5.0 \times$ ULN], whichever is lower, combined with [total bilirubin $> 2 \times$ baseline AND $> 2.0 \times$ ULN]	Mandatory: Permanently discontinue patient from study drug treatment. Repeat as soon as possible, preferably within 48 hours from awareness of the abnormal results, then with weekly monitoring of LFTs ^b), or more frequently if clinically indicated, until AST, ALT, or bilirubin have resolved to baseline or stabilization over 4 weeks.

All dose modifications should be based on the worst preceding toxicity.
 
^a Common Toxicity Criteria for Adverse Events (CTCAE Version 4.03)
 
^b Core LFTs consist of ALT, AST, GGT, total bilirubin (fractionated [direct and indirect], if total bilirubin $> 2.0 \times$ ULN), and alkaline phosphatase (fractionated [quantification of isoforms], if alkaline phosphatase $> 2.0 \times$ ULN.)
 
^c "Combined" defined as total bilirubin increase to the defined threshold concurrently with ALT/AST increase to the defined threshold
 
If combined elevations of AST or ALT and total bilirubin do not meet the defined thresholds, please follow the instructions for isolated elevation of total bilirubin and isolated elevation of AST/ALT, and take a conservative action based on the degree of the elevations (e.g. discontinue treatment at the situation when omit dose is needed for one parameter and discontinue treatment is required for another parameter). After all elevations resolve to the defined thresholds that allow treatment re-initiation, re-start the treatment either at the same dose or at one dose lower if criterion for dose reduction is met.
 
^d "Cholestasis" defined as ALP elevation ($> 2.0 \times$ULN and R value < 2) in patients without bone metastasis, or elevation of ALP liver fraction in patients with bone metastasis. The R value is calculated by dividing the ALT by the ALP, using multiples of the ULN for both values. It denotes whether the relative pattern of ALT and/or ALP elevation is due to cholestatic (R ≤ 2), hepatocellular (R ≥ 5), or mixed (R > 2 and < 5) liver injury.
 
^e "One dose level" defined as eltrombopag dose reduction by 25 mg.
	

